9.5 STUDY SIZE

In a previous study, 205.426 with over 1000 patients treated with Spiriva[®] Respimat[®], therapeutic success (i.e., 10-point increase in the PF-10 score between visit 1 and visit 2) was achieved in 61% of the patients.

In this study, a lower therapeutic success rate is expected as patients may be already on maintenance treatment at baseline. Assuming a 50% therapeutic success rate and 6510 patients, the 95% confidence interval for the therapeutic success rate would be between 48.8% (lower limit) and 51.2% (upper limit).

To account for a 7% drop-out rate, the sample size becomes 7000 patients.

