9.2 SETTING

It is planned that data of approximately 7000 patients from approximately 750 sites in 11 countries will be collected. Site selection will be performed to reflect routine COPD care in the participating countries in order to secure representativeness of the COPD population. The following countries will participate in this non-interventional study: Russia, Romania, Hungary, Austria, Czech Republic, Bulgaria, Slovenia, Croatia, Israel, Slovakia, and Switzerland.

A log of all patients included into the study (i.e. having given informed consent) will be maintained in the Investigator Site File (ISF) irrespective of whether they have been treated or not.

Boehringer Ingelheim reserves the right to discontinue the study or to remove a patient at a particular study site for the following reasons:

1. Failure to meet expected enrolment goals overall or at a particular study site.
2. Emergence of any efficacy/safety information that could significantly affect continuation of the study, or any other administrative reasons, i.e. lack of recruitment.
3. Violation of the protocol, the contract, or applicable laws and regulations for non-interventional studies, which could disturb the appropriate conduct of the NIS.

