9.7.3 Planned analyses

All patients who have received at least one dose of Spiolto® Respimat® will be included in the analysis; this is the treated set. All analyses will be performed on the treated set (as-treated analysis). If patients have missing values for an outcome, those patients will be excluded for that outcome's analysis.

The assessment will be carried out using SAS® software. The statistical characteristics presented in the end-of-text tables will be N / mean / SD / min / median / max for continuous variables. Tabulations of relative and absolute frequencies will be presented for categorical variables. Incidence rates and 95% CI will be given when appropriate.

The analyses will relate to the following data as recorded in the eCRF:

- Patient demographics (age, gender, height, and weight)
- Comorbidities
- COPD related and other concomitant medication
- History of smoking
- Reported exacerbations
- Breathlessness based on mMRC score
- Physical Functioning based on PF-10 scores (therapeutic success at visit 2); primary outcome
- Changes from visit 1 to visit 2 in the PF-10 score; secondary outcome
- Patient satisfaction with Spiolto® Respimat® at visit 2 only; secondary outcome
- General condition of the patient: evaluated by the physician (Physician's Global Evaluation (PGE)); secondary outcome
- Adverse Drug Reactions (ADR & SADR), fatal AEs, pregnancies
- GOLD spirometric classification (1,2, 3, 4)
- GOLD patient groups (A, B, C, D)
- Details of treatment with inhaled respiratory agents before the study
- Details of treatment with respiratory agents during the study

- Reasons for ending treatment during the observation period
- Details of treatment continuation / discontinuation

Main analysis

For the primary outcome, the proportion of patients with therapeutic success will be presented together with the 95% confidence interval.

Further analyses

The patient's general condition (PGE) at visit 1 and visit 2, mMRC at visit 1 and patient satisfaction at visit 2 are categorical variables so they will be analyzed as tabulations of frequencies. Change from visit 1 to visit 2 in the PF-10 score is a continuous outcome, so it will be analyzed with N / mean / SD / min / median / max.

The safety data will be reported according to local requirements.

As similar studies will also be performed in other European countries, data pooling might be considered at the end.

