9.10.1.3 Records

Case Report Forms (CRFs) for individual patients will be provided by the sponsor via remote data capture. All of the clinical data and site/investigator characteristics will be captured via a web-based Electronic Data Capturing system. The site staff will enter and edit the data via a secure network, with secure access features (username, password and secure identification – an electronic password system). A complete electronic audit trail will be maintained.

Patients must not be identified on the eCRF by name. Appropriately coded identification (i.e. Patient numbers) must be used.

All patient questionnaires will be paper-based and will be left at the site upon completion by the patient.

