6.5 POOLING OF CENTRES

This section is not applicable because centre/country is not included in the statistical model.

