7.3 PRIMARY ENDPOINT

For the primary endpoint, the percentage of patients with therapeutic success will be presented together with the 95% confidence interval. The number and percentage of patients with and without therapeutic success will be calculated for the whole FAS set [REDACTED]

[REDACTED]

[REDACTED]

[figure not shown]
The PF-10, represented by the physical functioning subscale of the Short Form 36 (SF-36), ranges from 0 to 100. A higher score indicates a better physical functioning. The score is calculated as followed:

Answer to questions 01- 10	Score
Yes, limited a lot	1
Yes, limited a little	2
No, not limited at all	3

Transformed scale = [(Sum of final item values – 10) * 100] / 20

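### The planned interval of 48.8% to 51.2% holds only for independent patients; the patients come from about 750 sites, and no visible text allows for within-site correlation

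*Protocol*

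**What the plan says.** - **Planned precision (protocol 9.5).** The basis is "Assuming a 50% therapeutic success rate and 6510 patients", and the protocol concludes that "the 95% confidence interval for the therapeutic success rate would be between 48.8% (lower limit) and 51.2% (upper limit". A 7% drop-out allowance brings the total to 7000. No formula, ICC or design effect is given.
- **Setting (protocol 9.2).** Data of "approximately 7000 patients from approximately 750 sites in 11 countries will be collected". On purpose: "Site selection will be performed to reflect routine COPD care in the participating countries in order to secure representativeness of the COPD population".
- **Reported interval.** Protocol 9.7.3: "For the primary outcome, the proportion of patients with therapeutic success will be presented together with the 95% confidence interval". SAP 7.3: "the percentage of patients with therapeutic success will be presented together with the 95% confidence interval". Neither names a method in visible text. SAP 7.3 is redacted directly after it refers to the full analysis set.
- **Centre (SAP 6.5).** "This section is not applicable because centre/country is not included in the statistical model".
- **Role of the interval.** Protocol 9.7.2 plans no hypothesis test, and SAP 7 calls all analyses descriptive.
- **Data held (protocol 9.10.1.3).** "All of the clinical data and site/investigator characteristics will be captured via a web-based Electronic Data Capturing system".

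**The concern.** Patients of one site share a physician, local prescribing habits, device training and the way the paper questionnaires are handed out. Their PF-10 responses may therefore resemble each other more than those of patients from different sites. The documents do not show that this happens here, but it is plausible.

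If it does, 6510 patients carry less information about the wider COPD population than 6510 independent patients would. The interval in 9.5 is the only precision statement that supports the study size. With no test planned, the 95% interval is also the visible statement of uncertainty for the primary endpoint. At stake is whether an interval labelled 95% has about that coverage. The estimated success rate itself is not at stake.

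**Working it through.** **Inputs from the documents.** p = 0.50 and n = 6510 (protocol 9.5); about 750 sites (protocol 9.2).

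**Inputs assumed, because the documents give neither.** ICC from 0.01 to 0.10; coefficient of variation (CV) of site size from 0 (equal sites) to 1 (very uneven).

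**Step 1: reproduce the plan's figure.** 1.96 × √(0.5 × 0.5 / 6510) = 1.21 points, so 48.79% to 51.21%. Wilson gives the same limits to two decimals; the continuity-corrected Wald and Clopper-Pearson intervals give 48.78% to 51.22%. All round to the stated 48.8% to 51.2%. The drop-out step is also right: 7000 × 0.93 = 6510. The planned interval is thus an independent-patient interval, and at this sample size the choice among standard binomial methods makes no visible difference.

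**Step 2: mean site size.** m = 6510 / 750 = 8.68.

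**Step 3: allow for clustering.**
- Design effect DE = 1 + ((1 + CV²) × m − 1) × ICC
- Half-width = 1.2146 × √DE
- Coverage of the unadjusted interval = 2Φ(1.96/√DE) − 1
- Effective sample size = 6510 / DE

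Example, ICC 0.05 with equal sites: DE = 1 + 7.68 × 0.05 = 1.384; half-width = 1.2146 × √1.384 = 1.43 points.

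| ICC | CV | DE | Half-width (points) | Interval | Coverage if unadjusted | Effective n |
|---|---|---|---|---|---|---|
| 0 | any | 1 | 1.21 | 48.8–51.2% | 95.0% | 6510 |
| 0.01 | 0 | 1.077 | 1.26 | 48.7–51.3% | 94.1% | 6046 |
| 0.01 | 1 | 1.164 | 1.31 | 48.7–51.3% | 93.1% | 5595 |
| 0.05 | 0 | 1.384 | 1.43 | 48.6–51.4% | 90.4% | 4704 |
| 0.05 | 1 | 1.818 | 1.64 | 48.4–51.6% | 85.4% | 3581 |
| 0.10 | 0 | 1.768 | 1.61 | 48.4–51.6% | 86.0% | 3682 |
| 0.10 | 1 | 2.636 | 1.97 | 48.0–52.0% | 77.3% | 2470 |

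With equal sites, an ICC above about 0.008 is enough to move the limits off 48.8 and 51.2 at one decimal: ((1.25/1.2146)² − 1)/7.68 = 0.0077.

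**Step 4: check that the remedy works.** A beta-binomial simulation used 6510 patients, 750 equal-sized sites, p = 0.5 and 4000 replicates (Monte Carlo error about 0.3 points near 95%). The 750 sites were spread over 11 countries in an assumed uneven layout.

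| ICC | Unadjusted coverage | Site-clustered coverage (country strata) | Mean clustered half-width (points) |
|---|---|---|---|
| 0 | 95.1% | 95.0% | 1.21 |
| 0.01 | 94.2% | 94.8% | 1.26 |
| 0.05 | 90.7% | 95.0% | 1.43 |
| 0.10 | 85.2% | 94.9% | 1.61 |

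Dropping the country strata changed coverage by no more than 0.1 point.

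**The case against.** **The reported interval may already be adjusted.** A reader might infer that the primary analysis will ignore clustering. The documents do not support that: SAP 7.3 is redacted in the very place where the interval is described, so its method is unknown. Only the planning interval in 9.5 is shown to be unadjusted. This objection stands, and the fix is worded accordingly.

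**SAP 6.5 does not settle it.** It might be read as a decision to disregard sites in the variance. It says only that centre and country are not model terms, in a section on pooling. It is silent on how the variance of a proportion is computed.

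**Not naming the method is not a defect in itself.** Step 1 shows that the standard binomial intervals agree. Only the treatment of clustering matters.

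**The target population is not fixed.** Sites are selected, not randomly sampled. If the target were only the success rate at the participating sites, between-site variation would not be sampling error. The half-width would then be about 1.2146 × √(1 − ICC): 1.18 points at ICC 0.05 and 1.15 at 0.10. The planned interval would be slightly conservative. The representativeness aim in protocol 9.2 favours the wider target but does not commit the plan to it.

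**The size is assumed, and nothing turns on it.** Both are true. There is no documented ICC, no site-size distribution, no test and no threshold.

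**Conclusion.** The point holds as a minor improvement. The interval in 9.5 is correct for independent patients, and no visible text allows for within-site correlation. The independence formula is too narrow on two conditions: that the result is meant to reach beyond these sites, and that the ICC is positive.

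Over the assumed range, the half-width rises by 0.05 to 0.76 points (1.26 − 1.21; 1.97 − 1.21). At ICC 0.01 with equal sites this is negligible. The 77.3% coverage needs both extreme assumptions together and should not be read as an expectation.

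For scale, if the planned 7% drop-outs were all failures or all successes, a 50% rate would become 46.5% (0.93 × 50) or 53.5% (46.5 + 7). Clustering is the smaller uncertainty, but it is one that a variance method can correct.

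A reader might also infer that the study is too small. That does not follow: the protocol sets no required half-width, and even 1.97 points is a precise estimate of a proportion near 50%.

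**What to change.** - **SAP 7.3.** Unless the redacted text already does so, compute the primary 95% interval around the crude proportion with a variance clustered by site, for example with SAS PROC SURVEYFREQ. Country strata are optional, since they brought no coverage gain in the simulation. If used, a country with a single site must be combined with another.
- **Protocol 9.5.** State that 48.8% to 51.2% assumes independent patients, and add the interval under a stated assumed ICC, for example 48.6% to 51.4% at ICC 0.05 with equal site sizes.

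If SAP 7.3 already specifies a clustered interval, only the change to 9.5 remains.

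**Cost.** One procedure call on site data already captured electronically, and a sentence in each document. The reported interval becomes slightly wider if the ICC is positive. If the ICC is zero, the mean half-width stays at 1.21 points but varies with an SD of about 0.03 to 0.04 points, because the variance is then estimated between sites. The point estimate and enrolment do not change.

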9.6 DATA MANAGEMENT

A data management plan (DMP) will be created to describe all functions, processes, and specifications for data collection, cleaning and validation. The electronic Case Report Forms (eCRFs) will include programmable edits to obtain immediate feedback if data are missing (also negative answers, unknown), out of range, illogical or potentially erroneous. These rules may encompass simple checks such as range validation or presence/absence of data. Concurrent manual data review may be performed based on parameters dictated by the DMP. Ad hoc queries to the sites may be generated and followed up for resolution. A source data quality audit may be initiated to ensure that the data in the database is accurate. Source data verification (SDV) will be performed at sites identified by a risk-based approach as needed.

The database will be housed in a physically and logically secure computer system maintained in accordance with a written security policy. The system will meet the standards of the

International Committee on Harmonization guideline E6R1 regarding electronic study data handling. Patient confidentiality will be strictly maintained.

9.7 DATA ANALYSIS

9.7.1 Statistical design – Model

Details will be described in the statistical epidemiological analysis plan (SEAP).

9.7.2 Null and alternative hypotheses

No formal hypothesis testing will be performed since this is a self-controlled study.

9.7.3 Planned analyses

All patients who have received at least one dose of Spiolto® Respimat® will be included in the analysis; this is the treated set. All analyses will be performed on the treated set (as-treated analysis). If patients have missing values for an outcome, those patients will be excluded for that outcome's analysis.

The assessment will be carried out using SAS® software. The statistical characteristics presented in the end-of-text tables will be N / mean / SD / min / median / max for continuous variables. Tabulations of relative and absolute frequencies will be presented for categorical variables. Incidence rates and 95% CI will be given when appropriate.

The analyses will relate to the following data as recorded in the eCRF:

- Patient demographics (age, gender, height, and weight)
- Comorbidities
- COPD related and other concomitant medication
- History of smoking
- Reported exacerbations
- Breathlessness based on mMRC score
- Physical Functioning based on PF-10 scores (therapeutic success at visit 2); primary outcome
- Changes from visit 1 to visit 2 in the PF-10 score; secondary outcome
- Patient satisfaction with Spiolto® Respimat® at visit 2 only; secondary outcome
- General condition of the patient: evaluated by the physician (Physician's Global Evaluation (PGE)); secondary outcome
- Adverse Drug Reactions (ADR & SADR), fatal AEs, pregnancies
- GOLD spirometric classification (1,2, 3, 4)
- GOLD patient groups (A, B, C, D)
- Details of treatment with inhaled respiratory agents before the study
- Details of treatment with respiratory agents during the study

- Reasons for ending treatment during the observation period
- Details of treatment continuation / discontinuation

Main analysis

For the primary outcome, the proportion of patients with therapeutic success will be presented together with the 95% confidence interval.

Further analyses

The patient's general condition (PGE) at visit 1 and visit 2, mMRC at visit 1 and patient satisfaction at visit 2 are categorical variables so they will be analyzed as tabulations of frequencies. Change from visit 1 to visit 2 in the PF-10 score is a continuous outcome, so it will be analyzed with N / mean / SD / min / median / max.

The safety data will be reported according to local requirements.

As similar studies will also be performed in other European countries, data pooling might be considered at the end.

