9. RESEARCH METHODS

9.1 STUDY DESIGN

This is a self-controlled study design enrolling consented COPD patients who will be treated with Spiolto® Respimat® according to the approved SmPC.

Patients will be enrolled consecutively and will be followed over an observational period of approx. 6 weeks. Data as listed in table 9.1:1 will be collected.

Table 9.1:1: Visit flow chart and data collection parameters

Parameter	Visit 1; baseline visit	Visit 2; approx. 6 weeks after baseline visit
Informed Consent	X	
Inclusion / Exclusion Criteria	X	
Patient demographics (age, gender, height, and weight)	X	
Start of COPD	X	
Number of exacerbations in the last 12 months	X	
Number of exacerbations leading to hospitalization in the last 12 months	X	
mMRC breathlessness scale, completed by the patient	X	
Past COPD therapies (6 months before visit 1)	X	
Respimat® training (yes/no)	X	
COPD severity based on GOLD assessment ¹	X	
Smoking status/history	X	X
Concomitant diseases / Comorbidities	X	X
COPD related and other relevant concomitant medication	X	X
Physical functioning (PF-10) questionnaire, completed by the patient	X	X
General condition of patient evaluated by Physician's Global Evaluation (PGE)	X	X
Safety: Adverse Drug Reactions (serious and non-serious), fatal AE, pregnancy	X	X
Patient satisfaction with Spiolto® Respimat®, completed by the patient		X
Rational for Spiolto® Respimat® treatment discontinuation (if applicable)		X
Continuation or discontinuation of treatment with Spiolto® Respimat® after the study (yes/no)		X

¹ GOLD patient group (A, B, C or D) will be automatically calculated within the eCRF based on available exacerbation history, mMRC, and GOLD spirometric classification of airflow limitation based on post-bronchodilator FEV₁ if available.

Baseline characteristics of patients being eligible and who gave Informed Consent, but were not treated in the study will also be collected.

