9.4 DATA SOURCES

Medical records collected through routine clinical care will be used to assess the inclusion/exclusion criteria of patients. Such medical records will be used for patient

demographics, smoking history, collection of previous COPD medication, concomitant diseases, and concomitant medication.

All patients will be enrolled consecutively.

The treating physician will use the Physician's Global Evaluation (PGE) to evaluate the general condition of the patient on an 8-point ordinal scale from 1 (very poor) to 8 (excellent). PGE will be completed before and approx. 6 weeks after treatment initiation.

The modified Medical Research Council (mMRC) scale will be used to assess the breathlessness state of the patient before the treatment. The mMRC stage (0 to 4) collected from the patient, as well as the exacerbation history and the post-bronchodilator FEV₁, will be used to automatically calculate the GOLD stage and patient group in the eCRF.

[figure not shown]
The physical functioning (PF-10) questionnaire is a subscale of the validated 36-Item Short Form Health Survey and contains 10 questions about everyday physical activity and functioning. Patients will be asked to complete the PF-10, in order to evaluate their physical functioning before and after treatment with Spiolto[®] Respimat[®].

A patient satisfaction survey will also be completed at the end of the study, using a 7-point ordinal scale with divisions from very dissatisfied to very satisfy.

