1 very dissatisfied 	2 dissatisfied 	3 rather dissatisfied 	4 neither satisfied nor dissatisfied 	5 rather satisfied 	6 satisfied 	7 very satisfied 
--	---	---	--	---	--	---

How satisfied are you with inhaling from the Respimat® device?

1 very dissatisfied 	2 dissatisfied 	3 rather dissatisfied 	4 neither satisfied nor dissatisfied 	5 rather satisfied 	6 satisfied 	7 very satisfied 
--	---	---	--	---	--	---

How satisfied are you with the handling of the Respimat® inhalation device?

1 very dissatisfied 	2 dissatisfied 	3 rather dissatisfied 	4 neither satisfied nor dissatisfied 	5 rather satisfied 	6 satisfied 	7 very satisfied 
--	---	---	--	---	--	---

4. Physicians' Global Evaluation (PGE) to be used directly within the eCRF

General condition of the patient at the initial examination (Visit 1)

Please mark with a cross as applicable

Poor
1 **2**

Satisfactory
3 **4**

Good
5 **6**

Excellent
7 **8**

General condition of the patient after approximately 6 weeks of treatment (Visit 2)

Please mark with a cross as applicable

Poor
1 **2**

Satisfactory
3 **4**

Good
5 **6**

Excellent
7 **8**

APPROVAL / SIGNATURE PAGE

Document Number: c03680587

Technical Version Number: 1.0

Document Name: clinical-trial-protocol

Title: Assessment of physical functioning and handling of Spiolto Respimat in patients with chronic obstructive pulmonary disease (COPD) requiring long-acting dual bronchodilation in routine clinical practice.

Signatures (obtained electronically)

Meaning of Signature	Signed by	Date Signed
Approval-Pharmacovigilance Representative		16 Nov 2015 16:32 CET
Author-Clinical Project		16 Nov 2015 16:33 CET
Approval-Team Member Medicine		16 Nov 2015 16:59 CET
Approval-Clinical		16 Nov 2015 17:30 CET
Author-Trial Statistician		16 Nov 2015 19:12 CET
Approval-On behalf of [REDACTED] or [REDACTED] or [REDACTED]		18 Nov 2015 16:06 CET
Approval-Team Member Medicine		18 Nov 2015 16:24 CET

(Continued) Signatures (obtained electronically)

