5.2 SECONDARY ENDPOINT(S)

- Absolute changes in PF-10 score from visit 1 to visit 2
- General condition of the patient, evaluated by the physician (PGE score) at visit 1 and visit 2
- Patient satisfaction with Spiolto® Respimat® at visit 2

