6.3 PATIENT SETS ANALYSED

Full analysis set (FAS): All screened patients with informed consent, date of registration, at least one documented administration of Spiolto® Respimat® and available PF-10 score at visit 1 and visit 2.

Treated set (TS): All screened patients with informed consent, date of registration and at least one documented administration of Spiolto® Respimat®.

Table 6.3: 1 Patient sets analysed

Class of endpoint	Patient set	
	TS	FAS
Primary and secondary endpoints		X
Safety endpoints	X	
Demographic/baseline	X	

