7.4 SECONDARY ENDPOINT(S)

All analysis will be descriptive and will be performed on FAS. For general condition of patients and patient's satisfaction with Spiolto® Respimat®, the number and percentage of patients within each category will be displayed. For absolute changes in PF-10 score, summary statistics will be provided.

[figure not shown]

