10. HISTORY TABLE

Table 10: 1 History table

Version	Date (DD-MMM-YY)	Author	Sections changed	Brief description of change
Draft v1.0	27-JUL-2016		None	This is the first Draft-Version of TSAP without any modification
Draft v1.1	11-AUG-2016		4-8	This is the second Draft-Version of TSAP. Besides adjustments in [REDACTED] analyses sets, documentation of AE was adapted
Draft v1.2	17-AUG-2016		7.3, 7.4, 8	This is the third Draft-Version of TSAP. Besides adjustments in planned statistical test, references were added
Draft v1.3	29-SEP-2016		3, 6.2, [REDACTED] 8	This is the fourth Draft-Version of TSAP. References have been updated.
Draft v1.4	14-OCT-2016		6.2	This is the fifth Draft-Version of TSAP. Display of ECadapted
Draft v1.5	19-OCT-2016		7.3, 7.4	This is the sixth Draft-Version.
Draft v1.6	21-OCT-2016		7.4	This is the seventh Draft-Version. Pooling of PGE and Satisfaction was added.
Draft v1.7	31-OCT-2016		7.4	This is the seventh Draft-Version.
Final 1.0	22-NOV-2016		[REDACTED]	[REDACTED]
Final 1.1	29-May-2017		3, 4	This is the first modification of the final version. References to CTP and TSAP were corrected

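### Does the plan need a visit 1 by visit 2 cross-tabulation of PGE because per-visit frequencies cannot show how many patients improved or worsened?

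*Protocol*

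**What the plan says.** Protocol section 9.1 describes the study this way: "This is a self-controlled study design". On the timing of the rating, Protocol section 9.4 says: "PGE will be completed before and approx. 6 weeks after treatment initiation". The scale has 8 points, and the form in Annex 3 groups them into four labelled bands of two points each.

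The secondary objective (Protocol 8.2) is to evaluate general condition at each of the two visits. The secondary outcome (Protocol 9.1.1) follows this, and so does the endpoint in SAP 5.2: "General condition of the patient, evaluated by the physician (PGE score) at visit 1 and visit 2". In the same lists, PF-10 is worded as a change from visit 1 to visit 2.

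For the analysis, Protocol 9.7.3 says: "The patient's general condition (PGE) at visit 1 and visit 2, mMRC at visit 1 and patient satisfaction at visit 2 are categorical variables", and plans frequency tables for them. For PGE and satisfaction, SAP 7.4 says that "the number and percentage of patients within each category will be displayed". The analysis is on the FAS, which SAP 6.3 assigns to "Primary and secondary endpoints". SAP section 7 makes all analyses descriptive and gives categorical tables a category for missing data.

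**The concern.** PGE is recorded twice on the same patient, and each patient's own baseline is the only comparator. Separate frequency tables for the two visits drop the pairing. They show how the group's distribution moved, and the mean change if the scores are treated as numbers. They do not show how many patients moved up, stayed or moved down. A reader could see an average gain without knowing whether few or many patients were rated worse after about 6 weeks. PF-10, the other outcome measured at both visits, does get within-patient summaries, so the plan can look uneven. What would be at stake is how informative one secondary outcome is; the primary result is not involved.

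**Working it through.** **1. The plan's own figures.** Protocol 9.5 gives a 95% CI of 48.8% to 51.2% for a 50% success rate in 6510 patients. The half-width is 1.96 × √(0.5 × 0.5 / 6510) = 0.0121, so the interval is 48.8% to 51.2%. For drop-out, 7000 × 0.93 = 6510. Both figures reproduce. Neither concerns PGE, and an added PGE table would change neither.

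**2. What per-visit tables leave open.** The documents give no PGE distribution, so these inputs are assumptions. Shares for scores 1 to 8:
- visit 1: 5, 10, 20, 25, 20, 12, 6, 2% (mean 4.15)
- visit 2: 2, 6, 12, 20, 25, 20, 10, 5% (mean 4.85)

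The mean change is 4.85 − 4.15 = 0.70 however the visits are paired. The individual moves do depend on the pairing. With a bivariate normal variable cut at these percentages, the results are:

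| Latent correlation | Improved | Unchanged | Worsened | Worsened on the four bands |
|---|---|---|---|---|
| 0.5 | 55.2% | 22.1% | 22.7% | 15.7% |
| 0.7 | 56.3% | 26.8% | 17.0% | 10.6% |
| 0.9 | 59.8% | 34.3% | 5.9% | 3.1% |

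These are correlations of the underlying normal variable. The 8-point scores themselves correlate at about 0.48, 0.67 and 0.87. If all 6510 patients had both ratings, 6510 × 0.227 ≈ 1,480 against 6510 × 0.059 ≈ 380 would be rated worse. The improved share moves only from 55.2% to 59.8%.

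**3. Limits without any correlation assumption.** Cumulative percentages are 5, 15, 35, 60, 80, 92, 98, 100 at visit 1 (call them P) and 2, 8, 20, 40, 65, 85, 95, 100 at visit 2 (call them Q).
- Smallest possible improved share: the largest P(k) − Q(k), which is 60 − 40 = 20% at score 4.
- Largest possible improved share: 100 minus the largest Q(k) − P(k−1), for example 20 − 15 = 5 at score 3, giving 95%.
- Smallest possible worsened share: 0%, because Q never exceeds P.
- Largest possible worsened share: 100 minus the largest P(k) − Q(k−1), which is 60 − 20 = 40 at score 4, giving 60%.

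So two per-visit tables do not fix the number of patients who improved or worsened. That part of the concern is correct.

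**4. Whether the plan promises those numbers.** Set the levels side by side:

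| Level | PGE | PF-10 |
|---|---|---|
| Objective (Protocol 8.2) | condition at visit 1 and at visit 2 | change in physical functioning |
| Outcome (Protocol 9.1.1) and endpoint (SAP 5.1, 5.2) | score at visit 1 and visit 2 | success from a 10-point increase; change between visits |
| Analysis (Protocol 9.7.3; SAP 7.3, 7.4) | number and percentage per category | success rate with 95% CI; summary of the change |

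Each column agrees from top to bottom. Where the sponsor wanted within-patient change as an outcome, it named it and planned an analysis for it. For PGE it named the state at each visit and planned tables that report that state. No stated quantity is left without an analysis, and no planned table misreports what it claims to show.

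**5. Whether the absence can be established.** The SAP contents list shows redacted entries, including one after 7.6 and one after section 8. The history table records several edits to 7.4. One entry, covering 7.3, 7.4 and 8, mentions a planned statistical test; another says "Pooling of PGE and Satisfaction was added". The visible 7.4 contains neither a test nor pooling. A log entry does not prove current content, and pooling alone would still give frequencies. It does mean that the visible paragraph may not be the whole PGE analysis.

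**The case for a change.** The best argument for the concern is that a self-controlled design exists to compare patients with themselves. PGE is the only secondary measure besides PF-10 taken at both visits, and the paired data are already collected. One more descriptive table would cost little, would conflict with nothing in the plan, and would fix in advance what counts as improved or worsened. All of that is true, and the non-identification shown above does not depend on the particular distributions assumed.

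It still describes a useful addition, not a fault. The within-patient comparison that the study is built on rests on PF-10, which is patient-reported and has both a responder rate with a CI and a change summary. PGE is a supporting rating by a physician who knows the treatment, in a study without a comparator. An improved/worsened split on it could not separate treatment effect from rating noise or regression to the mean. Counting any 1-point move as improvement or worsening also needs a threshold that the documents do not support. Frequency tables do not exclude a cross-tabulation at reporting, since such a table is itself a table of frequencies.

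**Conclusion.** The concern does not hold. PGE's objective, endpoint and planned analysis agree, and following the plan as written produces no wrong or biased result. There is no effect on the primary endpoint, the analysis sets, the 6510 evaluable patients or the total of 7000. What stands is narrow: per-visit tables alone do not give the number of patients rated better or worse. The size of that gap (5.9% to 22.7% worsened in the illustration) rests entirely on assumed distributions and latent correlations of 0.5 to 0.9. The plan does not set out to report that number. The conclusion rests on the visible text; if a redacted part of the SAP already contains a paired PGE table, even the wish for an extra table falls away.
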